Protocol

1. Project Title:

Predicting Response to Intra-Articular Corticosteroid Injection in Patients with Osteoarthritis of the Glenohumeral Joint

2. Investigators:

PI: [name].
Co-I: [name].
[name].
M. [name].
[name].
[name].
[name].
[name].
[name].
[name].
[name].

3. Abstract

In 2009, the AAOS made formal recommendations for osteoarthritis of the glenohumeral joint, but was unable to formally recommend physical therapy, pharmacotherapy or corticosteroid injection. Despite a lack of clinical evidence, orthopedic surgeons continue to recommend conservative treatments prior to considering surgical intervention for primary osteoarthritis of the glenohumeral joint. Generally, activity modification, over the counter analgesics, and intraarticular corticosteroid injections (IACSI) are offered prior to considering arthroplasty.^{5,6} The scientific literature remains limited regarding IACSI success for glenohumeral arthritis, with practices largely being adopted from the lower extremity literature. There remains only one small study assessing outcomes following IACSI, where success was indicated as significant pain reduction, improvement in the Constant-Murley scale, Shoulder Pain and Disability Index (SPADI) scores and satisfaction with treatment.³ The purpose of this study is to assess the effectiveness of IACSI for glenohumeral arthritis by 1) measuring clinical and radiographic parameters and 2) identifying predictors of IACSI success.

4. Background and Significance

Research regarding IACSI for glenohumeral OA is limited. While many articles have assessed the role of hyaluronic injections for this condition, only one study has assessed the effectiveness of IACSI.^{4,3,7,2} In this study, IACSI was retrospectively compared to intra-articular hyaluronic acid (HA) injections.³ All injections were administered in an unguided fashion. Corticosteroid dose for each injection was 40 mg of Depomedrol. Both groups received three injections one week apart, including the steroid group. Within the IACSI group, pain relief was only found to be significant at one month (6.25 vs 4.4, p=0.04). The clinical significance of this change remains debatable. This improvement was significant for both pain at night, as well as pain with activity. No significant differences remained at three months or six months. SPADI scores showed no significant changes over time. The range of motion

subscore of the Constant-Murley score remained significantly improved. They were unable to associate the grade of OA to pain relief following IACSI.

This study differs dramatically from clinical practice, where IACSI is normally administered as a single injection. Repeat injections are often delayed, with some surgeons recommending a three month break between injections. Presently, there is an evidence gap with respect to evidence of the effectiveness of single-injection IACSI on clinical and patient-reported outcomes in patients with glenohumeral OA.

5. Specific Aims

To address this deficit in the literature, there are two specific aims:

1. Assess the effectiveness of IACSI in patients with primary osteoarthritis in the shoulder. This will be determined through three patient-reported outcomes measures:
 - ASES (American Shoulder & Elbow Surgeon) score improvement > 20.9 points⁸
 - VAS (Visual Analog Scale) pain score improvement > 1.4 points
 - SST (Simple Shoulder Test) score improvement > 2.4 points
2. Assess clinical and radiographic predictors of success (outlined below) in patients who elect to receive IACSI as treatment for primary osteoarthritis in the shoulder.
 - Clinical
 - Duration of Symptoms
 - Location of pain (Anatomic Diagram, Figure 1)
 - Pain diagrams will be analyzed using a computer overlay protocol and analyzed in a binary matter according to region. Image software (NIH, Bethesda, MD) will be used. Proportions of the patients responding to injection in each anatomic region and groups of regions will be calculated. 95% confidence intervals will be determined.¹
 - History of prior injection
 - Range of motion (Forward elevation in the scapular plane, ER at 0° abduction, IR at 0° abduction)
 - Standardized pain and function scores (VAS pain, SST, ASES)
 - Prior analgesia (OTC, Narcotic)
 - Initial response to anesthetic component (VAS 5-10 min post-injection)
 - Radiographic
 - Joint space narrowing (measured)
 - Subluxation
 - Walch classification
 - Subchondral cysts
 - Samilson & Prieto Radiological Classification
 - Mild Arthrosis: inferior humeral and/or glenoid exostosis < 3mm in height

- Moderate Arthrosis: inferior humeral and/or glenoid exostosis measuring 3mm to 7mm slight gleno-humeral irregularity
- Severe Arthrosis: inferior humeral and/or glenoid exostosis measuring > 7mm gleno-humeral joint narrowing and sclerosis

6. Research Plan

Subjects: Five hundred patients, both male and female, age 18-100 years, with a diagnosis of symptomatic primary osteoarthritis of the shoulder will be recruited from the patient population seeking treatment at the Orthopaedics Sports Medicine Institute. Subjects enrolled into the study will be those who have failed previous treatment including over-the-counter analgesics and activity modification, and have elected to receive a medically-indicated, ultrasound-guided IACSI in the shoulder. Two or three plain film views of the shoulder (including a Grashey and axillary lateral) obtained in accordance with standard of care prior to enrollment in the study will be reviewed. Once written informed consent has been obtained, subjects will complete the pre-procedural pain chart (Figure 1), ASES, VAS pain (at rest, with activity, at night), and SST scores. Upon completion of all outcomes measures, the ultrasound-guided IACSI (5cc of 1% lidocaine, 2cc of depomedrol (40mg/mL)) will be administered. Subjects will be asked to repeat the VAS pain score (at rest) 5-10 minutes following administration of the injection to assess the response to the anesthetic component of the injection. Upon conclusion of the visit, no clinical follow-up appointment will be scheduled, and subjects will be instructed to follow-up with their physician as needed; this is in accordance with standard of care for this patient population.

MRN: _____
 Date: _____
 Diagnosis: _____
 Injection: _____
 Pain: Pre: _____ post: _____
 Global: Yes No

Please shade in the areas where you are feeling pain now.
 Please mark with a dark circle (●) the areas where the pain is the worst.

(Figure 1: Pre-procedural pain chart, anatomic diagram)

Subjects will be contacted via email through the REDCap survey function or a phone call at two weeks, one month, two months, three months, and six months following the injection to complete the ASES, VAS pain (at rest, with activity, at night), and SST scores. If an email survey is not completed in REDCap, a reminder email will be sent every two days, up to two

times. If, after the final email reminder, the REDCap survey is still incomplete, a member of the study staff will call the subject and complete the survey via telephone call.

Exclusion Criteria: Patients will be excluded from the study for any of the following reasons:

- Post traumatic osteoarthritis
- Inflammatory osteoarthritis
- Imaging confirmed rotator cuff tear
- Prior ipsilateral shoulder surgery
- Memory loss or inability to complete study measures
- History of allergy to injection medications
- Diabetic patients with patient-reported fasting blood glucose >200
- Prior injection in the ipsilateral shoulder within three months

Data Collection: The following data points and information will be collected for later analysis:

- Patient name
- MRN
- Gender
- Date of birth
- E-mail address
- Telephone number
- Location of pain (pre-procedural pain chart)
- Duration of symptoms
- History of prior IACSI in ipsilateral shoulder
- Prior analgesia
- Shoulder Range of Motion (Forward elevation, External rotation, Internal rotation)
- Radiographic findings
- Date of IACSI
- Date of each follow-up survey
- Results of each standardized pain and function survey

Confidentiality: Once all enrolled subject data is collected, subject PHI will be removed and the data will be maintained by using assigned research identification numbers that uniquely identify each individual. Date of birth will be converted to age, and dates will also be converted to time frames. Coded data will be stored on a secure online database such as REDCap and an Excel spreadsheet on a password protected computer within the Department of Orthopaedics and Rehabilitation. Data will be converted to a SPSS file for analysis which will also be stored on a secure department server. Data will be used only in aggregate and no identifying characteristics of individuals will be published or presented. Only the study team members will have access to these files. After the study is completed, local data will be stored with other completed research studies in a secured storage room until the appropriate time when the research files may be purged according to university policy.

Data Analysis:

Each patient-reported outcome measure will be assessed at each time point pre- and post-injection and grouped according to the grade of shoulder osteoarthritis. Groups will be compared using a one-way ANOVA analysis. Groups with a response to injection (VAS score improvements greater than the minimal clinically important difference) will be compared to those without a significant response. Single multi-level regression analysis will be performed to assess for clinical and radiographic risk factors outlined in Aim Two that may predict corticosteroid injection failure.

7. Possible Discomforts and Risks

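### Entry sets no minimum VAS, so a patient starting at 1.4 or below is classed as an injection failure even with complete relief

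*Combined protocol and SAP*

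**What the plan says.** Section 5, Aim 1, judges effectiveness by absolute improvements, among them "VAS (Visual Analog Scale) pain score improvement > 1.4 points" and "SST (Simple Shoulder Test) score improvement > 2.4 points". Section 6, Data Analysis, defines response as a VAS improvement above the minimal clinically important difference. Responders "will be compared to those without a significant response", and a regression then looks for the Aim 2 factors that predict failure of the injection. Data Analysis does not restate the threshold; I take it to be the 1.4 of Aim 1.

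Section 6, Subjects, enrols patients "with a diagnosis of symptomatic primary osteoarthritis of the shoulder will be recruited", and limits them to "those who have failed previous treatment including over-the-counter analgesics and activity modification" who have chosen a medically indicated injection. The list that opens "Patients will be excluded from the study for any of the following reasons" has eight entries, none of them a pain or function score. The baseline and follow-up assessments include "VAS pain (at rest, with activity, at night), and SST scores", so there are three VAS scores per visit, and the responder rule does not say which one it uses. No rule covers patients whose baseline leaves too little room to improve.

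**The concern.** The most a patient can improve is the distance from baseline to the best possible score. Where that distance is no larger than the threshold, the patient is a non-responder by arithmetic, and the failure group then mixes true non-response with no room to respond.

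This matters most for Aim 2, the purpose named in the study title. Radiographic grade, range of motion and prior narcotic use plausibly travel with baseline pain. If milder patients more often start at or below 1.4, mild grade or good motion can appear to predict failure when the injection works equally well at every grade.

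The symptomatic entry requirement does not close the gap. A patient with marked activity or night pain qualifies, yet may score 1.4 or less at rest. Rest is a live candidate for the responder score because it is the only version repeated 5-10 minutes after the injection.

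**Working it through.** **Inputs from the protocol.** VAS threshold: improvement above 1.4 (Aim 1). Planned number: 500 (Subjects). Only pain level given: 6.25, the starting value in the earlier study's steroid group, with no SD (Section 4). The protocol has no baseline distribution or response rate for this population, so there is no stated figure to reproduce.

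**Assumptions.** VAS 0-10 with 0 as no pain; baseline normal, truncated to 0-10; means and SDs as shown.

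**Step 1, who cannot respond.** Largest improvement = baseline - 0. It fails to exceed 1.4 when baseline <= 1.4. This step needs only the floor of 0.

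**Step 2, how many.** Share = [Φ((1.4-m)/s) - Φ((0-m)/s)] / [Φ((10-m)/s) - Φ((0-m)/s)].

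For m = 6.25, s = 2.5: (0.0262 - 0.0062) / (0.9332 - 0.0062) = 0.0216, and 500 x 0.0216 is about 11 patients.

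| Mean | SD | Share | Of 500 |
|---|---|---|---|
| 6.25 | 1.5 | 0.1% | 0 |
| 6.25 | 2.5 | 2.2% | 11 |
| 6.25 | 3 | 3.9% | 20 |
| 4 | 2.5 | 10.1% | 50 |
| 3 | 2.5 | 16.5% | 83 |

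**Step 3, effect on the response rate.** With a share f without room and a rate q among the rest, the observed rate is q(1-f), and the part of the failures that is arithmetic is f / [1 - q(1-f)]. Take q = 0.60 (assumed).
- f = 0.022: rate 0.60 x 0.978 = 58.7%; 0.022/0.413 = 5% of failures are arithmetic.
- f = 0.15: rate 0.60 x 0.85 = 51%; 0.15/0.49 = 31% of failures are arithmetic.

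**Step 4, effect on a predictor.** Suppose 60% of patients with room respond at every grade, but 15% of mild and 5% of severe patients have no room (all assumed). Failure is 1 - 0.60 x 0.85 = 49% in mild and 1 - 0.60 x 0.95 = 43% in severe disease. The odds ratio is (0.49/0.51)/(0.43/0.57) = 1.27, with no true difference between grades.

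**Step 5, cost of restricting.** I simulated no treatment effect at all: baseline and follow-up normal, clipped to 0-10, mean 3-4, SD 2.5, correlation 0.5-0.7 (all assumed). Improvement above 1.4 then occurs in 21-28% of all patients and in 26-36% of those starting above 1.4. Restricting to patients with room therefore adds regression to the mean.

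**The case against.** The strongest reply is that the group may be almost empty. Entry selects symptomatic patients in whom analgesics and activity modification have failed, and at the only pain level in the protocol the share is about 2% (SD 2.5). This stands as a limit on size. It does not settle the matter, because the responder VAS is unnamed and a rest score could sit much lower.

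A reader might infer that patients with high ASES or SST scores are also counted as failures. The documents do not support that. Response is defined by VAS alone, so a patient with an SST of 11 and enough VAS pain can still be a responder.

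A reader might also infer that Aim 1 will report three success rates, each pulled down by a different amount. That is one possible reading. Aim 1 does not say that per-patient proportions will be reported, and Data Analysis assesses each measure over time and compares osteoarthritis grades by ANOVA. The 51% against 60% in the working is therefore an illustration, not an expected bias.

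Baseline VAS, SST and ASES are listed as Aim 2 predictors. If they enter the model together with grade and motion, they weaken the distortion of those other factors. They do not remove the problem, because low baseline pain then predicts failure partly by construction.

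Finally, restricting the analysis has its own bias, as Step 5 shows. This is a good reason not to replace the all-patient rate with the restricted one.

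**Conclusion.** The point holds for the VAS responder rule. As written, the rule places any patient with a responder VAS of 1.4 or below in the failure group, including one whose pain disappears entirely. That conclusion rests on a VAS floor of 0 and on reading the threshold in Data Analysis as the 1.4 of Aim 1.

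Its size is not known. The shares of about 0-4% and 10-17% depend on assumed SDs and, for the second, on assumed means. That a material number of patients will start this low is a possibility, not something the protocol shows. The issue merits a cheap improvement: it needs no new data, and the count itself will show whether it matters.

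**What to change.** In Data Analysis:
- name which VAS version (rest, activity or night) defines response;
- report the number of patients whose baseline on that version is 1.4 or below;
- keep the all-patient response rate, and show beside it the rate among patients with baseline above 1.4;
- run the responder versus non-responder comparison and the failure regression with the no-room patients left out of the failure group, alongside the all-patient result.

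If per-patient success proportions are also reported for ASES and SST under Aim 1, give the same count and restricted rate. On the usual ranges (assumed: ASES 0-100, SST 0-12 in whole items, high is best), success is impossible from ASES 79.1 or above (100 - 20.9). On SST it is impossible from 10 or above, because exceeding 2.4 takes at least 3 items.

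The cost is a few lines of text using scores already collected, with no change to enrolment or follow-up. The downsides are a slightly smaller denominator that differs by scale, and more regression to the mean in the restricted rate. The second is why the all-patient rate stays beside it.

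### Later injection in, or surgery on, the study shoulder is not recorded, so the plan cannot separate a single injection's effect from usual care with re-treatment, mainly at six months

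*Combined protocol and SAP*

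**What the plan says.** The Background (section 4) sets the question: "there is an evidence gap with respect to evidence of the effectiveness of single-injection IACSI".

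Under the Research Plan (section 6), each of 500 patients receives one ultrasound-guided injection, after which "no clinical follow-up appointment will be scheduled, and subjects will be instructed to follow-up with their physician as needed". Contact is then by email or telephone at two weeks and at one, two, three and six months. These surveys are described as ASES, VAS pain and SST only.

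The Data Collection list has injection history before entry, one injection date, the date of each survey, and "Results of each standardized pain and function survey". No item covers an injection or operation on the study shoulder after the index injection. The exclusions for previous surgery on that shoulder, and for an injection into it in the preceding three months, are entry criteria.

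Under Data Analysis, "Each patient-reported outcome measure will be assessed at each time point pre- and post-injection". Patients are then split by response: "Groups with a response to injection (VAS score improvements greater than the minimal clinically important difference"), against those without. A regression looks for predictors of injection failure. Aim 1 (section 5) puts the VAS threshold at more than 1.4 points. The plan sets no condition on intervening treatment and names no survey at which response is classified.

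**The concern.** The protocol makes both kinds of re-treatment foreseeable. On injections, the Background says: "Repeat injections are often delayed, with some surgeons recommending a three month break between injections". On surgery, the Abstract (section 3) says that "intraarticular corticosteroid injections (IACSI) are offered prior to considering arthroplasty". The Background also reports that in the one earlier study, which used a different regimen of three weekly injections, the steroid group's pain benefit was no longer significant at three or six months. Some patients may therefore seek further treatment within follow-up.

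Under the plan as written, a patient whose pain returned, who was re-injected and who then scored above the threshold is coded as a responder. Nothing in the data set would show that this happened. Two results are at stake: the six-month responder rate read as the effect of one injection (Aim 1), and the predictor analysis (Aim 2), where the same patient sits on the wrong side of the split if the question is response to a single injection.

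**Working it through.** **1. What can be reproduced.** The plan gives no responder rate, re-treatment rate or power calculation. Its only usable inputs are n = 500, the 1.4-point threshold and the survey times. Every rate below is an assumption.

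**2. Timing of a repeat injection.** After a break of about three months, a repeat given within follow-up falls between the three- and six-month surveys. At the six-month survey it is at most 6 − 3 = 3 months old, which is the window the protocol treats as disqualifying at entry. This break is only what some surgeons recommend. A shorter interval would reach earlier surveys, and a longer one could fall after month six and touch none. No timing is given for surgery.

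**3. Effect on the responder rate if only failures are re-treated.** Let
- p = six-month response without re-treatment,
- r = share of failures re-treated,
- q = share of those who then pass the threshold.

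Observed rate = p + (1 − p) × r × q.

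- Example A, p = 0.3, r = 0.2, q = 0.5: 0.7 × 0.2 × 0.5 = 0.07, so 37% is observed against 30%. With all 500 answering, there are 350 failures, 70 are re-treated and 35 change category. For scale, the 95% half-width at 30% is 1.96 × √(0.3 × 0.7 / 500) = 0.040, or about 4 points.
- Example B, p = 0.5, r = 0.02, q = 0.3: 0.5 × 0.02 × 0.3 = 0.003, or 0.3 points.

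**4. What that formula leaves out.** It can only raise the rate. Let t be the share of responders operated on before the survey and u the share of those who then score below the threshold. The net shift is (1 − p) × r × q − p × t × u, which is negative whenever the second term is larger. The documents give nothing from which to set t or u.

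**5. Effect on a predictor.** Assume response without re-treatment of 40% in mild and 20% in severe disease, and q = 0.5. The odds ratio is (0.40/0.60) / (0.20/0.80) = 2.67.

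| Failures re-treated (mild / severe) | Observed response | Odds ratio |
|---|---|---|
| 20% / 20% | 0.46 vs 0.28 | 2.19 |
| 10% / 30% | 0.43 vs 0.32 | 1.60 |
| 30% / 10% | 0.49 vs 0.24 | 3.04 |

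The odds ratio moves towards or away from 1 depending on who is re-treated.

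**The case against.** **As-observed response is legitimate.** Aim 1 speaks of the effectiveness of the injection, and care follows usual practice. In such a cohort the as-observed rate answers a real question. This stands: 37% in Example A is not wrong as a usual-care result. But the stated gap concerns a single injection, and without a record of re-treatment the two results cannot be told apart.

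**The size is conjectural and the exposure narrow.** For repeat injection the exposure is mainly one survey of five. It matters for Aim 2 only if response is classified there, and the plan does not say. This also stands, and it limits the conclusion. However, the size is unknown partly because the planned data cannot measure it.

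**The information could be recovered.** The medical record number is collected, and identifiers are kept until data collection ends: "Once all enrolled subject data is collected, subject PHI will be removed". Chart review is therefore possible, but none is planned and treatment elsewhere would be missed. In Example A, finding half of the re-treatments leaves 0.07 × 0.5 = 3.5 points, and finding 80% leaves 0.07 × 0.2 = 1.4 points.

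**The survey forms are not shown.** They might hold a re-treatment question. The text describes only the standard scores, and the Data Collection list has no such item.

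**Counting re-treated patients as non-responders is itself biased.** This is true. It makes care-seeking part of the outcome, so it should be one of two reported definitions and not the only one.

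**Conclusion.** The point holds. The plan neither records re-treatment of the study shoulder nor says how to handle it, so it cannot separate the single-injection effect from usual care with re-treatment. Confidence is high about the missing record and rule. There is no basis for confidence about the size: Examples A and B give 7 points and 0.3 points on assumed rates, and the true shift could be near zero.

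A reader might infer more than this, in three ways:
- **That six-month success will be overstated.** That follows only if re-treatment goes mostly to failures and helps them. Surgery shortly before a survey could lower observed response.
- **That predictor effects will be diluted.** Step 5 of the working shows movement in both directions.
- **That repeat injections will fall between months three and six.** The protocol reports a practice of some surgeons. It sets no study rule and gives no frequency.

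The plan should be changed on this point, because the gap bears on its stated question and the remedy is cheap. It does not invalidate the as-observed results, provided they are described as usual-care results.

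**What to change.** 1. **Record it.** Add two dated yes/no questions to each existing email or telephone survey: another injection in this shoulder, and surgery on this shoulder. Word both to cover the whole period since the study injection, so that a missed survey does not lose the event. Supplement with chart review by medical record number before identifiers are removed.
2. **Define response in advance.** Name the survey at which response is classified. Report the responder and predictor analyses, including the prior-injection predictor, under two pre-stated definitions: re-treated patients counted as non-responders from the date of re-treatment (single injection), and as observed (usual care).
3. **Keep the continuous scores.** Report them as observed, labelled as usual-care results, with counts of re-treated patients by grade and time point. The ANOVA by grade will still include re-treatment effects, and the label should make that plain.

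**Cost.** Two short questions, a chart check and a paragraph of analysis text, with no added visit and no change to care. Reported single-injection success at six months may be lower. The non-responder definition also counts as failures those patients who repeat an injection to keep a benefit. If 10% of responders did so, 30% would be reported as 0.30 × 0.90 = 27%.

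The prior-injection predictor is the most exposed. Assume that it has no true effect, with 30% responding in both groups:
- If 20% of responders with a prior injection and 5% of those without repeat, the non-responder definition gives 0.240 vs 0.285, OR 0.79.
- If 30% and 10% of failures are re-treated and half then pass, the as-observed definition gives 0.405 vs 0.335, OR 1.35.

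Neither definition is safe alone, which is why both should be shown.

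### Aim 1 asks whether patients improve, but the only test named for the scores compares arthritis grades, and no whole-cohort change or responder proportion is planned

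*Combined protocol and SAP*

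**What the plan says.** Section 5 gives Aim 1 as "Assess the effectiveness of IACSI in patients with primary osteoarthritis in the shoulder". It ties this to three improvement thresholds: more than 20.9 points on ASES, more than 1.4 on VAS pain, and, for the third, "SST (Simple Shoulder Test) score improvement > 2.4 points". Each is a change within a patient.

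The Data Analysis paragraph of section 6 has four sentences:

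1. "Each patient-reported outcome measure will be assessed at each time point pre- and post-injection and grouped according to the grade of shoulder osteoarthritis".
2. "Groups will be compared using a one-way ANOVA analysis".
3. Patients who respond, defined by "VAS score improvements greater than the minimal clinically important difference", are compared with those who do not. No test is named.
4. A regression looks for the Aim 2 predictors of injection failure.

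The only responder proportions with 95% confidence intervals are under the pain-location predictor of Aim 2: "Proportions of the patients responding to injection in each anatomic region and groups of regions will be calculated".

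Section 6 (Subjects) collects ASES, "VAS pain (at rest, with activity, at night), and SST scores" at baseline and again at "two weeks, one month, two months, three months, and six months following the injection".

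**The concern.** The named test and the aim ask different questions. Aim 1 asks whether patients improve after the injection, and by enough to matter. A one-way ANOVA between grades asks whether the grades differ from one another at a given visit. A large benefit shared by all grades would give null ANOVAs throughout.

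Followed as written, the study can finish without an estimate, confidence interval or test for the first of its two aims. The ASES and SST thresholds in Aim 1 are not used in the Data Analysis at all. The VAS threshold is used only to form two groups for comparison.

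The gap also leaves room for selection after the data are seen. Many score-by-visit results could be put forward as the effectiveness finding. None is named as the main one, and no VAS item is tied to the 1.4-point threshold.

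A secondary point applies only if the ANOVA is run on raw scores, which is the plainer reading, though change scores are not excluded. A difference between grades before the injection would then carry into each follow-up comparison and could be mistaken for a difference in response.

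**Working it through.** The plan gives no SD, alpha, power or sample-size derivation, so there is no figure of its own to reproduce.

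**Inputs from the protocol.** N = 500 in one cohort; thresholds 20.9, 1.4 and 2.4; five follow-ups; three VAS items plus ASES and SST.

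**Assumptions, not in the documents.** Three grades, normal scores, two-sided alpha 0.05, VAS SD 2.5 (range 2.0-3.0), correlation with baseline 0.6 (range 0.3-0.7), and all 500 patients answering unless stated.

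**1. The ANOVA cannot see shared improvement.** The between-grade sum of squares is Σ nᵢ(x̄ᵢ − x̄)². Subtract a constant c from every score: each x̄ᵢ and the overall x̄ fall by c, the differences stay the same, and so does F. This holds for any SD, correlation or grade mix.

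Simulation with 2,000 replicates and near-equal grades confirms it:

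| Uniform improvement | ANOVA, raw scores | ANOVA, change scores | Paired test, whole cohort |
|---|---|---|---|
| 0, 1.4 or 3.0 points | 4.0-6.0% | 4.7-5.8% | about 100% at 1.4 and 3.0 |

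A separate simulation (4,000 runs per scenario, grade shares 40/35/25, correlation 0.5, N = 500 and 300) used VAS improvements of 1.4 and 5, ASES 20.9 and SST 2.4. The ANOVA rejected in 4.7-5.7% of runs and the paired test in 100%. With no improvement the ANOVA rejected in 4.5-5.1% and the paired test in about 5%.

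**2. Raw scores only: baseline gaps carry forward.** Suppose nobody changes and the grade means differ from the start by −0.5/0/+0.5. The noncentrality is λ = N Σ wᵢ(μᵢ − μ̄)²/SD², where wᵢ are the grade shares. With equal grades and SD 2.5, λ = 500 × 0.1667/6.25 = 13.3. The chance of rejection follows from the noncentral F with 2 and 497 df:

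| Gap and grade mix | SD 2.0 | SD 2.5 | SD 3.0 |
|---|---|---|---|
| ±0.5, equal | 98.8% | 91.3% | 78.0% |
| ±0.5, 20/30/50 | 98.0% | 88.7% | 74.1% |
| ±0.5, 10/30/60 | 92.8% | 76.8% | 60.0% |
| ±0.25, equal | 51.9% | 35.1% | 25.4% |

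On change scores the rate is about 5%.

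**3. Precision that the planned data could give.**

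- Mean VAS change: SD of change = SD × √(2(1 − r)) = 2.5 × √0.8 = 2.24. Half-width = 1.96 × 2.24/√500 = 0.20 points. SD 2.0 with r 0.7 gives 0.14; SD 3.0 with r 0.3 gives 0.31.
- Responder proportion: half-width = 1.96 × √(p(1 − p)/500), which is 4.0 percentage points at p = 0.3 or 0.7 and 4.4 at p = 0.5.
- With 300 patients answering, the same formulas give 0.18-0.40 VAS points and 5.2-5.7 percentage points.

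**4. Number of candidate results.** (3 VAS items + ASES + SST) × 5 follow-ups = 25.

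**The case against.** The strongest reply is that Aim 1 already states all three responder criteria, and that splitting patients by VAS improvement yields a responder count as a by-product. Responder proportions with confidence intervals are also planned for pain regions and for groups of regions. On this view a four-sentence paragraph is merely terse. The regression is described as multi-level, and if its levels are visits within patients it could carry a time term.

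Part of this stands. An overall VAS responder proportion could be derived, and the criteria are fixed in advance. But nothing commits the team to report that figure, and no analysis applies the ASES or SST criterion. The regional proportions belong to a predictor in Aim 2, and the plan ties the regression to Aim 2 risk factors for failure.

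Three further objections limit how much weight the numbers carry:

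- The 4-6% rejection rates are simply alpha. That is correct: they illustrate an identity and are not evidence about this cohort.
- The baseline-gap figures rest on assumed gaps and apply only to raw scores. That is also correct. A gap would show in the pre-injection ANOVA, and baseline scores are candidate predictors in the Aim 2 regression, so this stays secondary and confined to the ANOVA.
- Full response is optimistic for remote surveys with no scheduled clinic visit. At 300 respondents the intervals widen but remain narrow enough to judge change against 1.4 points.

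Comparing grades is a legitimate question. It is not Aim 1.

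**Conclusion.** The concern holds, and the plan should be corrected before analysis. The one test named for the scores answers a different question from the one Aim 1 poses, and no whole-cohort change or responder proportion is committed to for any of the three scores. This conclusion needs no assumption about SDs, correlation or grade mix, because a shift common to all grades leaves F unchanged.

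The baseline carry-over (60-99% false signals for gaps of ±0.5, 25-52% for ±0.25 with equal grades) depends on raw scores being used and on assumed gaps and SDs. The main conclusion does not rest on it. The precision figures depend on the assumed SDs and correlations and on how many patients answer.

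**What to change.** Rewrite the Data Analysis paragraph and the wording of Aim 1 as follows.

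- For each score at each of the five follow-ups, report the mean within-patient change from baseline with a 95% CI, and the proportion of patients exceeding 20.9, 1.4 or 2.4 points with a 95% CI. Give the number of patients behind each figure.
- Name in advance one main follow-up visit, and say which VAS item (rest, activity or night) carries the 1.4-point threshold.
- For the grade comparison, replace the visit-by-visit ANOVAs with one repeated-measures model of change per score, with terms for visit, grade and grade by visit. Baseline adjustment and a linear contrast across grades are optional refinements.
- Because there is no comparator, word the Aim 1 conclusion as change after injection.

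The cost is some redrafting and a little more analysis work, with no new data or visits. The team accepts a more modest conclusion and must commit to one visit and one VAS item beforehand.
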